demographic questionnaire, a parent-report of the child's tic severity called the Parent Tic Questionnaire (PTQ), and a rating scale of ADHD severity called the Swanson Nolan and Pelham Scale-4th edition (SNAP-IV). After completing the video observation protocol, children will be asked to complete a child-report of tic severity called the Child Tic Questionnaire (CTQ), a self-report Premonitory Urge for Tics Scale (PUTS) to measure the child's global premonitory urge, and a self-reported rating scale of puberty development called the Peterson Puberty Development Scale (PDS). For female participants who have had first menses, a pregnancy screen will be conducted. Interested participants who meet full eligibility criteria will be invited back to complete Visit 2 (HRT session) approximately 1 week later.

At Visit 2, participants will arrive and will be randomly assigned to receive either a 50 mg placebo pill or a 50 mg d-cycloserine pill. Evaluating clinicians, participants, and the therapist will be blind to randomization assignment, with only the study coordinator and research pharmacy having access to randomization assignment. As d-cycloserine typically takes 1 hour to become active in participants' system, children and adult will be re-administered the following rating scales to evaluate the current severity of the participant's tics, most bothersome tics, and premonitory urge: the CTQ; PTQ, HM/VTS and I-PUTS. Children will then be asked to complete a computer task to evaluate habit learning called the Weather Prediction task. Afterwards, children will complete a session of HRT that will target two tics in treatment as identified by the HM/VTS. After the participant has completed the session of HRT, the participant will be asked to practice the skills learned in the session over the next week and to document practices using a homework monitoring form. The therapist will complete a session summary sheet to evaluate the patient's mastery of the skills within session. After the completion of the HRT session, a standard side effect form will also be administered to the participant to assess for any side effects. Participants will be asked to return 1 week later for a follow-up assessment. Visit 2 may take up to 4 hours to complete.

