At Visit 3, participants will complete a battery of tic assessment to monitor change in tic severity. These assessments will be administered by a clinician blind to randomization assignment, and will include the YGTSS, I-PUTS, HM/VTS, and the Clinical Global Impression of Improvement that serves as a global rating of improvement of tics. Participants will also be administered a standard side effect form to monitor for any possible side effects of d-cycloserine. Children will complete a standardized 10 minute video observational protocol to identify the frequency and severity of tics (Himle et al. 2006). Parents will be asked to complete the PTQ to assess parent report of tic severity and a homework compliance monitoring form to evaluate the participant's practice of skills learned in HRT over the past week. Children will be asked to complete the CTQ to assess child-reported tic severity and the PUTS to evaluate their premonitory urge globally. Children will also complete a homework compliance form. This visit may take up to 2 hours. Participants and their families will be collectively compensated \$30 for each study visit.

Tests/Measures Administered:

The following measures and tasks will be administered this study.

Clinician Administered:

Anxiety Disorder Interview Schedule-Parent and Child Version (ADIS-C/P; Silverman & Albano, 1996). This is a clinician-administered, structured diagnostic interview based on DSM-IV diagnostic criteria. Diagnoses reflect endorsement of symptoms as well as a severity rating (patient impairment/distress) of at least 4 on a 0-8 scale. The tic disorder section, created

by [name], will be used to confirm tic diagnoses. The ADIS-C/P is widely used in both research and practice.

Yale Global Tic Severity Scale (YGTSS; Leckman et al., 1989). The YGTSS is a semi-structured interview that examines the presence and severity of motor and phonic tics over the previous week across 5 domains: total motor tics, total phonic tics, total tics, overall impairment rating, and a global severity score. The YGTSS has well-supported psychometric properties (Storch et al., 2005; Leckman et al., 1989).

Individualized Premonitory Urge for Tics Scale (I-PUTS). The I-PUTS is a clinician-administered scale that assess the frequency, intensity and body region of premonitory urges that are associated with tics endorsed on the YGTSS.

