Clinical Global Impression – Severity (CGI-S; Guy, 1976). The CGI-S is a 7-point clinician rating of illness severity that is anchored by 0 (no illness) and 6 (extremely severe). The CGI-S will be used as an overall measure of tic severity.

Clinical Global Improvement (CGI; Guy, 1976). The CGI is a clinician-rated measure of treatment response on a 7-point scale ranging from 1 ("very much improved") to 7 ("very much worse"). Response status is defined as a rating of "very much improved" or "much improved" and based on the participant's level of overall tic severity relative to baseline (Visit 1).

Hopkins Motor/Vocal Tic Scale (Walkup et al. 1992). Participants nominated up to five motor and five vocal tics they deemed most bothersome. These tics are rated by a clinician on a 5-point scale that ranged as follows: 0 (none), 1 (mild), 2 (moderate), 3 (moderately severe), and 4 (severe). These ratings incorporated frequency, forcefulness, interference, and subject distress. Participants are also asked about whether a premonitory urge is associated with each bothersome tic.

Adverse Event Review Form. A modified version of the Safety Monitoring Uniform Report Form will be completed at Visit 2 and Visit 3 to monitor for any possible adverse events or side effects from the single administration of d-cycloserine or placebo.

Direct Observation Video Recordings:

Direct Observation of Tics (Himle et al., 2006). An observed tic frequency count will be obtained through partial-interval scoring of a 10 minute video recording of participants. After video observation is collected, raters will record the number of 10-second intervals during which participants have at least one tic. Ten-second intervals are most commonly used in tic studies and this method of scoring has been shown to be highly correlated with total tic frequency (Woods et al., 1996, 2003; Himle et al., 2006).

Computer Tasks:

The Weather Prediction Task (Knowlton, Squire & Gluck, 1994). The Weather Prediction task is a measure of procedural or habit learning that requires gradual acquisition of stimulus-response associations. Participants are asked to predict rain or sunshine based on the presentation of a varying combination of a set of four different cards on a computer screen by pressing one of two letters on the keyboard. Each card is independently and probabilistically related to the

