outcomes, each of which occurs equally often. Participants receive positive or negative feedback after each prediction via visual feedback on the computer screen. The task consists of 90 trials lasting approximately 15 minutes. Accuracy (% correct) and reaction time scores across six learning blocks were used as the outcome variables.

Parent Report Forms:

Demographic Form. A demographic form will assess information regarding the participant's age, gender, ethnicity, living situation, parental marital status, parental income, and parental occupational status. Additionally, the form will assess the participant's past treatment history and whether they have taken medications and for what duration of time. Finally, this demographic form also inquires about the participant's health including whether the participant has an unstable medication condition, is pregnant or breast feeding, and/or has a history of a seizure disorder, kidney disease, or liver disease.

Parent Tic Questionnaire (PTQ, Chang et al. 2009). The PTQ is a 28 item measure comprised of 14 commonly experienced motor tics and 14 commonly experienced vocal tics. Parents are asked to identify whether each of these tics have been absent or present over the past week for their child. For tics that are endorsed over the past week, parents are asked to make a separate rating of the frequency and intensity of the tic on a 1-4 scale. Items are summed separately for motor tics and phonic tics, with all items summed for a total parent-reported rating of tic severity over the past week.

Swanson Nolan and Pelham-4th Revision (SNAP-IV, Swanson, 1992). The psychometrically sound, parent-rated SNAP-IV (Swanson, 1992) provides a dimensional scaling of the *DSM* items for inattention, impulsivity, hyperactivity, oppositionality, and related behaviors. Symptoms are scored by assigning a severity estimate for each item on a 4-point scale.

Parent Reported Homework Compliance. The parent-reported homework compliance form consists of 9 questions that ask about the parent's perception of the child's duration of practice over the past week, and the child's mastery over the skills learned in HRT across settings (home and school).

Child Report Forms:

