For the purposes of this study, an adverse event is any untoward medical occurrence associated with the use of a drug in humans, whether or not considered drug related.

For the purposes of this study, a serious adverse event is characterized as any adverse drug event (experience) occurring at any dose that in the opinion of the study investigator results in any of the following outcomes: (1) death, (2) life-threatening adverse drug experience, (3) inpatient hospitalization or prolongation of existing hospitalization (for > 24 hours), (4) persistent or significant incapacity or substantial disruption of the ability to conduct normal life functions, (5) congenital anomaly/birth defect, and (6) important medical event (IME) that may jeopardize the subject and may require medical or surgical intervention to prevent one of the outcomes listed in this definition.

Procedures will be used to monitor subject safety

Adverse events will be systematically assessed at Visits 2 and 3 using a standardized adverse event review form (i.e., modified version of the Safety Monitoring Uniform Report Form). This will allow study investigators to monitor for any possible adverse events or side effects from the single administration of d-cycloserine or placebo.

Who (list names) will identify, document, and report adverse events?

The study PI will identify and document adverse events when they have been identified during the study.

What is the frequency for review of summarized safety information and who will perform the review?

Any serious, unanticipated problems (e.g., serious adverse events) will be reported to the IRB within 3 working days of study investigators' awareness.

What are the stopping rules with regard to efficacy and safety?

In the event of a serious adverse event, the subject will discontinue study participation and the attending psychiatrist (the prescribing physician) will be notified. The research staff will monitor the participant closely until the adverse reaction remits.

10. Potential Risks of Study Participation

The risks of participating in this project include relatively lengthy psychiatric evaluations, participating in a single session of HRT, and the medication (placebo or DCS).

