Finally, the potential side effects associated with the administration of DCS include drowsiness, headache, prolonged or momentary dizziness, seizures, confusion, hallucinations, weakness, coma, rash, vitamin B₁₂ deficiency and/or folate deficiency (both of which may cause weakness and anemia), liver enzymes increases (which could cause weakness or bleeding), and shaking. However, these side effects are most commonly related with doses greater than 500mg/day and when dosed chronically (versus acutely), which is at least ten times greater than what we propose to administer in this study. DCS has been approved by the Food and Drug Administration for the treatment of tuberculosis for over 20 years, and, as discussed by Rothbaum et al. 2008, single-pill administrations have been associated with no adverse effects. Furthermore, a recent meta-analysis of over 20 randomized controlled trials of DCS-augmentation that included multiple doses of DCS within each trial, identified no greater adverse event profile relative to placebo with as many as 8 trials reporting no adverse events at all. In the event of a moderate or severe adverse event related to the medication, the subject will be withdrawn from the study, the attending psychiatrist ([name] will be notified), and the research staff will monitor the participant closely until the adverse reaction remits.

Although not a risk directly associated with d-cycloserine, there is always the chance that a participant may report either the perceived risk of suicidality or suicidality itself. In these cases, standard protocol will be followed. If, during an assessment, research staff determines that a

youth endorses a serious mental health program such as suicidal behavior, referral information and telephone numbers to appropriate community services will be provided. The PI will conduct a risk assessment for suicidal ideation and/or behavior. Although unanticipated, if the detected problem is imminent and of crisis status, the PI will take appropriate immediate action including calling emergency services and/or calling UCLA campus police to escort the youth to the emergency department (on-site at UCLA). These situations will be reviewed immediately with the PI's research mentor ([name]), who is a licensed clinical psychologist.

11. Analysis Plan

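### The adverse event form is first completed after the pill and the HRT session, so there is no recorded pre-dose reference for separating existing symptoms from new ones

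*Combined protocol and SAP*

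**What the plan says.** Section 8 (Procedures) puts dosing at the start of Visit 2: "At Visit 2, participants will arrive and will be randomly assigned to receive either a 50 mg placebo pill or a 50 mg d-cycloserine pill". While the drug takes effect, the tic and urge scales are repeated, then come the Weather Prediction task and the HRT session. Only then does the safety form appear: "After the completion of the HRT session, a standard side effect form will also be administered to the participant to assess for any side effects". One week later, at Visit 3, it is given again: "Participants will also be administered a standard side effect form to monitor for any possible side effects of d-cycloserine".

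Two other places confirm this schedule. The entry for the Adverse Event Review Form in Section 8 (Tests/Measures Administered) reads "A modified version of the Safety Monitoring Uniform Report Form will be completed at Visit 2 and Visit 3", and Section 9 reads "Adverse events will be systematically assessed at Visits 2 and 3 using a standardized adverse event review form". The Visit 1 battery does not include the form.

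Section 9 defines an adverse event broadly, whether or not it is thought to be caused by the drug, and sets no condition on onset or on worsening from a prior state. Section 10 lists expected effects of DCS that include drowsiness, headache, dizziness, weakness, confusion and shaking.

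**The concern.** Several of the symptoms listed in Section 10 are common and non-specific, and the eligible children have other reasons to have them. Section 6 of the eligibility logic, set out under Inclusion/Exclusion Criteria in Section 8, allows stable non-antipsychotic medication and co-occurring psychiatric disorders, and Section 11 expects some children to be on alpha-2 agonists. A child who arrives with a headache, or drowsy on existing medication, may be entered on the form after the session with nothing on file to show that the symptom came first.

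Two things are at stake. The count of children with a possible side effect can be too high in both arms. And when the investigator considers whether one child's symptom came from the pill, no pre-dose observation supports the judgement. The plan takes pre-treatment ratings of the targeted tics at Visits 1 and 2, but no corresponding reading on the safety form.

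**Working it through.** **Step 1: is there a pre-dose reading anywhere?** Measures listed before or around dosing, set against the symptoms in Section 10:

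| Measure | Where | Records current headache, drowsiness, dizziness? |
|---|---|---|
| ADIS-C/P, YGTSS, I-PUTS, HM/VTS, CGI-S, video observation | Visit 1 | No: diagnoses, tics, urges |
| PTQ, CTQ, PUTS, SNAP-IV, PDS | Visit 1 | No: tics, urges, ADHD, puberty |
| Pregnancy screen | Visit 1 | No |
| Demographic form | Visit 1 | No: treatment and medication history and specific conditions |
| Repeated scales | Visit 2 | No: tics and urges only |
| Adverse Event Review Form | Visit 2 after HRT; Visit 3 | Possibly, but only after the pill |

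The Visit 2 repeat consists of rating scales for tics and "premonitory urge: the CTQ; PTQ, HM/VTS and I-PUTS". The nearest thing to a health baseline is in the parent form: "this demographic form also inquires about the participant's health including whether the participant has an unstable medication condition". It also covers pregnancy and breast feeding, and seizure, kidney and liver disease. It is a screen for exclusions and does not ask about current symptoms. I take the side effect form in the visit descriptions to be the Adverse Event Review Form; the visits match.

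**Step 2: how much could this move the counts?** The documents give no adverse event rate and no safety figure to reproduce. The sample is up to 20, set by feasibility. What follows is an illustration under these assumptions:

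- 10 children per arm (the allocation ratio is not stated);
- no drug effect and no new symptoms;
- a share p of children has at least one form symptom before the pill, and each such child is recorded.

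Let A and B be the counts in the two arms, independent Binomial(10, p). Then P(|A − B| ≥ 2) = 1 − P(A = B) − P(|A − B| = 1).

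| p | Expected per arm (10p) | P(A = B) | P(difference of 1) | P(difference ≥ 2) |
|---|---|---|---|---|
| 5% | 0.5 | 0.463 | 0.426 | 0.11 |
| 10% | 1 | 0.313 | 0.444 | 0.24 |
| 20% | 2 | 0.224 | 0.382 | 0.39 |

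The chance that at least one of 20 children has a pre-existing symptom is 1 − (1 − p)^20: 64%, 88% and 99%.

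**Step 3: how much would a pre-dose form remove?** Some symptoms also begin after the pill for reasons other than the drug. Take p = 20% pre-existing and an independent share q of new background symptoms. Without a pre-dose form, the recorded share is 1 − (1 − p)(1 − q). With perfect separation it is q.

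| q | Recorded share without the form | P(difference ≥ 2) without | P(difference ≥ 2) with |
|---|---|---|---|
| 10% | 1 − 0.8 × 0.9 = 28% | 45% | 24% |
| 20% | 1 − 0.8 × 0.8 = 36% | 48% | 39% |
| 30% | 1 − 0.8 × 0.7 = 44% | 50% | 46% |

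The gain in the between-arm comparison runs from sizeable to small, depending on a second unknown rate. The gain in reading an individual child's record does not depend on either rate.

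**The case against.** The strongest reply is that the form's content is not shown. It is listed among the clinician-administered measures, and a clinician could ask whether a headache began before the pill. That stands. A reader might infer that pre-existing symptoms cannot be told apart from new ones. The documents support less: they do not say how the two are separated, and they provide no pre-dose record. Asking about onset afterwards would rely on recall, in children as young as 8, at the end of a visit of up to 4 hours.

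The placebo arm also answers part of the concern. With blinding and randomisation, existing symptoms fall equally on the arms on average, so there is no bias between them. Section 11 plans no adverse event comparison, so no stated analysis is damaged. And the chance differences above mostly reflect 10 children per arm, as Step 3 shows.

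A reader might further infer that existing symptoms will cause children to be withdrawn. The rule in Section 10 is "In the event of a moderate or severe adverse event related to the medication, the subject will be withdrawn from the study". It needs an event that is moderate or severe and also judged related to the medication, so an existing symptom would meet it only if misattributed. The documents give no ground for saying how often that would happen.

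Finally, a pre-dose form does not remove fatigue that builds up during the visit after the pill. That also stands.

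**Conclusion.** The gap is real and rests on the text alone: every place that schedules the form puts it at Visit 2, where its only stated time is after the HRT session, and at Visit 3, and no other listed measure records the relevant symptoms before dosing. The consequence is limited. Counts in both arms can be inflated, and attribution in the individual child lacks recorded support; any between-arm comparison remains unbiased on average but noisy. The 11%, 24% and 39% figures depend on the assumed prevalence, equal arms and complete recording of existing symptoms, and should be read as scale only. This is a cheap improvement to the safety record. It does not undermine the primary analysis.

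**What to change.** Administer the same Adverse Event Review Form on arrival at Visit 2, before the pill, in both arms. Visit 1 would not serve: it is about a week earlier and would miss a symptom present on the day. Continue to record every adverse event as Section 9 defines it. In addition, report by arm the items that are new or worse than on the pre-dose form, so that reporting is not narrowed.

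This needs a sentence in each of the Visit 2 procedures, the form's entry under Tests/Measures Administered, and Section 9, plus a line in Section 11 for the by-arm summary. The cost is a few minutes at an existing visit.

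Separately, Section 9 ties discontinuation to a serious adverse event, while Section 10 ties withdrawal to a moderate or severe event related to the medication. The two passages must be reconciled.

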One potential risk of participating in this project includes discomfort associated with the psychiatric evaluation and administration of rating scales – either due to the discussion of subjectively difficult topics, or due to the length of time required for the interviews and questionnaires. In efforts to minimize subject burden, we only chose measures that were central to study questions and did not overlap considerably with other study measures. With regard to potential discomfort, our experience indicates that most people welcome the opportunity to discuss their experiences with a trained clinician; and any information shared by the subject will be kept confidential. Additionally, we have done our best to minimize subject burden while assessing relevant constructs and maintaining the internal validity of the study. Breaks will be given as much as possible to decrease boredom and physical/psychological discomfort. As well, we will compensate families \$30 for each study visit. This compensation will be split equally between parent and child participants.

Another possible risk is that participants may feel subjective distress when learning skills to manage their tics as part of habit reversal training (HRT). This effect is usually very transitory and mild, and though to be a result of the participant gradually habituating to a distressing internal sensation referred to as a premonitory urge. This effect of HRT will not be described as an adverse event, unless a subject or parent specifically describes the reaction as an adverse event of participation. However, in general, participants in randomized controlled trials (RCTs) find HRT to be beneficial in learning to manage their tics, with no significant adverse events reported (Piacentini et al. 2010).

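### Section 10 lets the family's wording decide whether distress during HRT counts as an adverse event, which conflicts with the Section 9 definition

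*Combined protocol and SAP*

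**What the plan says.** Section 9 (Safety Monitoring Plan) gives the definition: "an adverse event is any untoward medical occurrence associated with the use of a drug in humans, whether or not considered drug related". On collection it says: "Adverse events will be systematically assessed at Visits 2 and 3 using a standardized adverse event review form". On who decides, it says: "The study PI will identify and document adverse events when they have been identified during the study".

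Section 10 (Potential Risks of Study Participation) warns that children may be distressed while learning to manage their tics in HRT. It adds "This effect is usually very transitory and mild" and puts the effect down to gradual habituation to the premonitory urge. It then sets the rule: "This effect of HRT will not be described as an adverse event, unless a subject or parent specifically describes the reaction" in those terms.

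Section 8 (Study Procedures) places the pill before the HRT session within Visit 2 and says: "After the completion of the HRT session, a standard side effect form will also be administered to the participant to assess for any side effects". A side effect form is given again at Visit 3. The therapist's session summary sheet records urge habituation and mastery of the competing response.

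Section 11 (Analysis Plan) names no adverse event comparison.

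**The concern.** An adverse event count is useful only if the same occurrence is counted in the same way for every child. Under Section 10, two children with the same reaction are classified differently if one parent calls it an adverse event and the other calls it a hard session. The rule also settles the cause in advance, for a reaction that arises after dosing in a blinded drug trial.

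The trial's own descriptive safety record in children aged 8 to 17 is at stake. A statement that few or no adverse events occurred would partly reflect the families' vocabulary. Classification also has a second use: Section 10 ties withdrawal from the study to an adverse event of at least moderate severity that is judged related to the medication. A reaction never classed as an adverse event may not reach that judgement.

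**Working it through.** The plan states no figure on this point. The sample size rests on feasibility, and no rate of distress or of adverse events is given. The check is therefore a comparison of the texts.

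1. **Test by cause.** Section 9 makes attribution irrelevant. Section 10 removes one class of reaction because it is presumed to come from HRT. The two rules give different answers for any distress that is untoward.

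2. **Who decides.** Section 9 gives identification to the principal investigator, supported by a standardized form. Section 10 makes the child's or parent's choice of term decisive.

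3. **Scope of the exception.** The description of the reaction is qualified by *usually*, but the exclusion that follows is not. Read literally, marked or prolonged distress during HRT is also left out unless the family uses the label.

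4. **Can the cause be known for one child?** Sections 7 and 8 put the pill first and HRT second at the same visit, and every child receives both. Distress during HRT therefore follows dosing in both arms, and no individual observation separates the two. Section 4 says that HRT works through extinction and associative learning and that DCS enhances both; Section 10 links the distress to habituation to the urge. An effect of DCS on this distress is thus plausible from the stated mechanism. The documents do not assert one, and its direction is unknown.

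5. **Do other records fill the gap?** In part. The form is given after HRT and at Visit 3, and Section 8 says it covers adverse events and side effects. Its items are not shown, so whether it asks about distress cannot be determined. The session sheet covers habituation and mastery, which are not distress. No named measure records distress in the session.

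6. **Effect on the count.** Let *p* be the probability in an arm of distress that meets the Section 9 definition, and *s* the share of families who use the label. The recorded probability is *p* × *s*. If *s* is the same in both arms, the difference between arms becomes *s* × (*p* for DCS − *p* for placebo). Both counts, and any difference in either direction, shrink by the factor *s*. The documents give neither *p* nor *s*, so no number is attached.

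**The case against.** The best defence is that Section 9 requires an untoward medical occurrence. Mild, brief discomfort that is part of the therapy falls below that threshold, and family report is a safety valve that only adds cases. Part of this stands: not every moment of discomfort in HRT should become an adverse event, and the correction should keep the word untoward. But the defence does not explain why a family's wording would turn something that is not untoward into something that is. Nor does it cover distress that is more than mild.

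Three further objections stand, and each blocks a stronger reading.

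- A reader might infer that the rule hides the distress. The documents do not support that. The rule governs what is called an adverse event, not what is asked, and the side effect form is still given twice.
- A reader might infer that this is the event most likely to show an interaction between drug and therapy. Nothing in the documents ranks it so. Section 10 does not list distress among the DCS side effects, and faster habituation could as well shorten it.
- A reader might infer that a planned safety comparison is biased. Section 11 plans none, the rule applies equally to two blinded arms, and up to 20 children would support little formal comparison even with complete recording.

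**Conclusion.** The conflict between Sections 9 and 10 is real and lies in the current text. It is a stated rule, not a missing detail: untoward distress after dosing is excluded by presumed cause, without a severity or duration limit, unless the family applies a particular label. The descriptive adverse event count can therefore be incomplete and depends on wording.

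The size cannot be estimated from the documents, and any numerical illustration would rest on invented rates. No planned efficacy or safety analysis changes. The conclusion assumes that some distress during HRT would meet the Section 9 definition, which the qualifier on severity in Section 10 leaves open. It does not depend on DCS having any effect on distress. The point is worth correcting because the change is small and the participants are minors.

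**What to change.** - Reconcile Sections 9 and 10 by deleting the family-label exception.
- Record untoward distress during or after HRT on the existing Adverse Event Review Form at Visits 2 and 3, with its severity and a tag such as *expected, HRT-associated*, whatever the presumed cause and whatever the family calls it.
- Add to Section 11 that tagged and untagged events will be reported descriptively by arm.
- State how this classification relates to the Section 10 withdrawal rule, which depends on adverse event status. Those passages must be reconciled; no clinical rule is proposed here.

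The cost is a sentence removed from Section 10, a short addition to Section 11, a clarification of the link to withdrawal, and one field on a form already in use. The downside is that more mild, expected events will be recorded in both arms; the tag keeps them separable from the rest.
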